1.2 Schedule of Assessments

Following screening, informed consent, and confirmation that a patient with severe COVID-19 meets all eligibility criteria, subjects will be randomized 1:1 to receive duvelisib 25 mg, po BID or a placebo pill, po BID. Randomization between duvelisib 25 mg po BID and placebo BID will be stratified by study site. The investigational pharmacy will supply coded study drug based upon the results of central randomization.

Procedures and Tests Study Tests DURING HOSPITALIZATION [#]	Days -2 to 0 [@]	Day 1 [@]	Day 8 (± 2)	Day 15 (± 2)	Day 29 (± 3)	Day 50-60
Randomization to duvelisib or placebo arm	X					
Study Drug Administration		Oral drug BID Days 1-14				
SARS-CoV-2 RT-PCR	X					
Immunophenotyping of immune cells in blood		X	X	X	X	
Whole blood for RNA gene expression ^{##}		X	X	X	X	
Mononuclear cells for mass cytometry ^{##}		X	X	X	X	
Plasma cytokines and chemokines ^{##}		X	X	X	X	
Anti-SARS Cov-2 IgG		X			X	
TSH	X				X	
Hepatitis Serologies if known history of treated Hepatitis B or C	X					

Standard of Care Tests*	Days -2 to 0	Day 1	Day 8 (± 2)	Day 15 (± 2)	Day 29 (± 3)	Day 50-60
Physical Exam	X	Performed daily during hospitalization				
ECOG Performance Status	X	Performed daily during hospitalization				
Vital Signs	X	Performed daily during hospitalization				
Clinical Labs: Record data in eCRF (REDCap) during hospitalization as shown below						
CBC with differential	X	Abstract data as available				
CMP	X	Abstract data as available				
Ferritin		Abstract data as available				
CRP, Troponin		Abstract data as available				
Coagulation Tests**		Abstract data as available				
Non-contrast Chest CT or Chest X-Ray	X	Abstract data as available				
Serum or Urine Pregnancy Test***	X					
Assessment of Survival Status						X

study procedures which are performed as part of the research protocol and covered by the study budget

Additional research blood samples will be obtained prior to discharge from hospital

@ Some overlap of procedures and tests performed for screening and Day 1 is expected.

* Standard of care procedures which are routinely performed on COVID-19 patients and the results of which will be recorded as part of study conduct

** PT/INR, PTT, Fibrinogen, D-Dimer, Heparin/Enoxaparin Anti Xa

*** Pregnancy test for WOCBP may be obtained after hospital admission but prior to study enrollment

2. Objectives (and Endpoints)

OBJECTIVES	ENDPOINTS
Primary	

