4.2.3. Product Storage and Stability

Duvelisib/placebo will be stored at the Emory Investigational Pharmacy. Duvelisib/study drugs will be stored at room temperature between 20-25 degrees Celsius.

4.2.4. Study Drug Administration:

Duvelisib/placebo is an oral medication that will be taken twice a day. The intent of the study design is to conduct a placebo-controlled double-blinded/double-masked administration of duvelisib or placebo in hospitalized

Protocol Title: Duvelisib Ameliorates Manifestations of Pneumonia in Established Novel Coronavirus Infection (DAMPEN-CI)

patients with severe COVID-19. All efforts will be undertaken to maintain ignorance among clinical and study staff as to allocation of each individual patient to active drug versus placebo—Subjects, the clinical team (physicians, nurses, advanced practice providers (nurse practitioner/physician assistant), clinical pharmacists) will not be informed as to whether an individual subject is receiving active drug or placebo.

4.2.5 Interruption/Disruption of Treatment:

Duvelisib/placebo is a BID medication. Medication doses that are missed or not absorbed (i.e., vomiting) will not be made up with additional dosing.

Duvelisib can be stopped if any of the following are observed:

- Grade 3 or 4 hematologic toxicity (19) as defined by the NCI CTCAE v5.0.
- Grade 3 or 4 non-hematological toxicity

Study drug (duvelisib or placebo) will be stopped at the time of hospital discharge if that occurs prior to day 15.

Grades 1-2 AEs as defined by the NCI CTCAE, version 5.0 will not result in any dose modifications and will be treated with supportive care. If study drug is stopped due to an AE, it will not be resumed.

5. Study Procedures

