8.1 Duration of therapy and follow up

In the absence of treatment delays due to adverse event(s), subjects will be treated for 14 days with duvelisib/placebo. A subject will be considered to have completed the study if he or she has completed all phases of the study including the last visit or the last scheduled procedure shown in the schedule of activities. Subjects who have signed consent, are deemed eligible and are randomized to receive study drug (duvelisib/placebo) will be considered evaluable for efficacy endpoints on an intent-to-treat basis. Subjects who receive at least one dose of study drug (duvelisib/placebo) will be evaluable for toxicity. The end of the study is defined as completion of the last visit or procedure in SOA (Day 29) and an assessment of survival status on day 50 - 60. In the event of a subject's withdrawal, the Investigator will make every effort to complete the End of Treatment procedures specified in the Schedule of Events. Subjects who withdraw from the study will be encouraged to permit follow-up for clinical end-points, including death, mechanical ventilation (e.g. intubation, high-flow O₂ Bi-PAP or AIRVO), hospital discharge, and need for supplemental oxygenation. Subjects will be assessed daily while hospitalized. If the subjects are discharged from the hospital, they will have phone follow-up calls with a study team member at

Protocol Title: Duvelisib Ameliorates Manifestations of Pneumonia in Established Novel Coronavirus Infection (DAMPEN-CI)

day 15 (window d13 – 25), and at day 29 (window d27 - 39) for clinical outcomes data. Arrangements will be made for an outpatient phlebotomy appointment after day 29 (day 30 - day 60 if possible, but up to day 100) to obtain safety laboratory tests and blood samples for secondary research. Patients will receive \$100 compensation for the in-person follow-up phlebotomy visit. However, travel distance, infection control or other restrictions may limit the ability of the subject to return to the clinic. In such cases, only clinical data will be obtained via the d27 - 39 call.

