At the interim analysis (20 patients/arm), the incidence of death or mechanical ventilation, grade ≥ 3 elevations in liver transaminases, or neutropenia will be estimated. We assume that the underline rate is 40%, 10%, or 24% for the three incidences in placebo group respectively, and if the rate in duvelisib group is $\geq 15\%$ higher than that in the placebo group in either of the three incidences, the trial may be stopped due to the safety concern. It also translates to stop the study if 3 or more excess events in duvelisib group are observed in either of the three incidences. Operating Characteristics, the probability of trial stopping due to ≥ 3 excess events based one simulation study, is listed in the below table.

AEs	Underline event rate in Placebo arm	Underline event rate in Duvelisib arm						
		5%	10%	20%	30%	40%	50%	60%
death or mechanical ventilation	40%	0%	0.02%	0.7%	4.8%	16.6%	37.4%	62.7%
grade ≥ 3 elevations in liver transaminases	10%	0.79%	5.7%	32.8%	65.8%	87.9%	97.2%	99.7%
neutropenia	24%	0.07%	0.6%	7.3%	26.1%	52.7%	77.3%	92.6%

In addition to the study stopping rules based an interim analysis, the Independent Data Monitoring Committee (IDMC) will review, on a monthly basis, the number of Grade 3 and/or Grade 4 adverse events in each arm, including neutropenia and elevated transaminases, and consider stopping or suspending accrual to the study if the frequencies of Grade 3 or Grade 4 adverse events are significantly higher among subjects in the duvelisib arm compared with subjects in the control arm.

Analysis of Safety Data

The primary safety endpoints include death or mechanical ventilation, grade ≥ 3 elvation in liver transminases, and neutropenia within 4 weeks. The cumulative incidence rate of each safety endpoint will be calculated with 95% confidence interval by randomized arms, and compared by Fisher's exact test.

Handing of Missing Data

For the safety endpoints and secondary endpoints, missing data will not be imputed, summaries and analyses will be based on the observed cases. For the primary efficacy analysis, every effort will be made from the informed consent form design to clinical follow up to reduce the missing data. Patients withdraw consent before the primary endpoint can be measured will be replaced.

Demographics and Baseline Characteristics

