16.1 Safety Analyses

Adverse event data will be described and graded per the NCI CTCAE v5.0 guidelines. For AE that are not listed in the NCI CTCAE v5.0 guidelines, grade 3 AEs are defined as events that interrupt usual activities of daily living, or significantly affects clinical status, or may require intensive therapeutic intervention. Severe events are usually incapacitating. For each adverse event, information to be collected includes event description, time of onset, clinician assessment of severity, relationship to study product (assessed only by those with the training and authority to make a diagnosis), and time of resolution/stabilization of the event. Regardless of relationship, all AEs will be recorded with start dates occurring any time after patient receives any duvelisib/placebo. At each study visit, the investigator will inquire about the occurrence of AE/SAEs since the last visit. Events will be followed for outcome information until resolution or stabilization.

Any medical condition that is present at the time that the participant is screened will be considered as baseline and not reported as an AE. However, if the study participant's condition deteriorates at any time during the study, it will be recorded as an AE. Changes in the severity of an AE will be documented to allow an assessment of the duration of the event at each level of severity to be performed. AEs characterized as intermittent require documentation of onset and duration of each episode.

The maximum grade for each type of toxicity will be recorded for each patient, and frequency tables will be reviewed to determine toxicity patterns. Adverse events will be summarized and described within each cohort. They will initially be reviewed regardless of attribution, but also whether they are possibly, probably, or definitely related to treatment. In addition, we will review all adverse event data that are graded as 3, 4, or 5 and classified as either "unrelated" or "unlikely to be related" to study treatment in the event of an actual relationship developing. The incidence of severe adverse events or toxicities will be described. We will assess the proportion of patients who experience grade 3 or higher non-hematologic toxicity. To assess tolerability, we will also capture the proportion of patients who go off treatment due to adverse events.

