16.2 Adverse Event and Serious Adverse Event Reporting

Definition of Adverse Events (AE)

The ICH defines an adverse event as any unfavorable and unintended sign, including laboratory findings, symptoms or diseases temporally associated with the use of an investigational product. Adverse event severity will be graded per the using the CTCAE version 5 for toxicity and adverse event reporting.

Protocol Title: Duvelisib Ameliorates Manifestations of Pneumonia in Established Novel Coronavirus Infection (DAMPEN-CI)

Any adverse events, either observed by the investigator or reported by the patient, should be documented, including the intensity and duration of the AE, what steps were taken in regard to duvelisib and the outcome.

The principal investigator must review any laboratory abnormality for clinical significance. If the abnormality is deemed to be clinically significant, then the adverse event will be reported along with the actions taken in regard to duvelisib and the outcome of the event. All AE's will begin recording at the beginning of enrollment until withdrawal and/or completion of the clinical trial.

Definition of Serious Adverse Events (SAE)

An adverse event (AE) or suspected adverse reaction is considered "serious" if, in the view of either the investigator or sponsor, it results in any of the following outcomes:

- Death
- Life-threatening adverse event
- Inpatient hospitalization or prolongation of existing hospitalization
- A persistent or significant incapacity or substantial disruption of the ability to conduct normal life functions, or a congenital anomaly/birth defect.
- Important medical events that may not result in death, be life-threatening, or require hospitalization may be considered serious when, based upon appropriate medical judgment, they may jeopardize the participant and may require medical or surgical intervention to prevent one of the outcomes listed in this definition. (Examples of such medical events include allergic bronchospasm requiring intensive treatment in an emergency room or at home, blood dyscrasias or convulsions that do not result in inpatient hospitalization, or the development of drug dependency or drug abuse).

Study-Specific AE/SAE Reporting

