An **unexpected** adverse event occurs when the nature or severity or frequency of the event is not consistent with the risk product's information (i.e., investigator's brochure, not listed on the informed consent document).

Documenting Adverse Events

From the time of treatment until 14 days following cessation of duvelisib/placebo all adverse events, that begin or worsen after informed consent, **must be recorded** by the investigator or designee at each examination on the Adverse Event case report forms (CRF)/worksheets

The investigator will make every attempt to follow all subjects with non-serious adverse events for outcome. Conditions that were already present at the time of informed consent should be recorded in the Medical History page of the patient's CRF/worksheet.

Adverse events will be assessed and graded according to the Common Terminology Criteria for Adverse Events (CTCAE) version 5.0. Grade 1 to 5 will be used to characterize the severity of the Adverse Event. If CTCAE grading does not exist for an adverse event, the severity of mild, moderate, severe, and life-threatening, death related to the AE corresponding respectively to Grades 1 - 5, will be used. Information about any deaths (related to an Adverse Event or not) will also be collected. The occurrence of adverse events should be sought by non-directive questioning of the patient (patient) during the screening process after signing informed consent and at each visit during the study. Adverse events also may be detected when they are volunteered by the patient (patient) during the screening process or between visits, or through physical examination, laboratory test, or other assessments. As far as possible, each adverse event should be evaluated to determine:

1. The severity grade (CTCAE Grade 1-5)
2. Its duration (Start and end dates)
3. Its relationship to the study treatment (Reasonable possibility that AE is related: No, Yes) or Its relationship to the study treatment (Reasonable possibility that AE is related: No, Yes)
4. Action taken with respect to study or investigational treatment (none, dose adjusted, temporarily interrupted, permanently discontinued, unknown, not applicable)
5. Whether medication or therapy was given (no concomitant medication/non-drug therapy, concomitant medication/non-drug therapy)
6. Whether it is serious, where a serious adverse event (SAE) is defined as in Section 16.1 and which seriousness criteria have been met).

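### The plan states three different ends to adverse event recording, and the shortest one observes early stoppers for less than the 4-week safety period

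*Combined protocol and SAP*

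**What the plan says.** Three statements in the combined protocol and SAP govern how long AEs are recorded.

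- Section 16.1, Safety Analyses, sets no end: "all AEs will be recorded with start dates occurring any time after patient receives any duvelisib/placebo".
- Section 16.2, Definition of Adverse Events: "All AE's will begin recording at the beginning of enrollment until withdrawal and/or completion of the clinical trial".
- Section 16.2, Documenting Adverse Events, gives the rule for case report form entry, which ties the end to the last dose: "From the time of treatment until 14 days following cessation of duvelisib/placebo all adverse events" that begin or worsen after consent must be recorded.

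The analysis horizon is fixed. Section 15.1, Analysis of Safety Data, lists death or ventilation, grade 3 or higher transaminase elevation, "and neutropenia within 4 weeks". Arms are compared by Fisher's exact test, and missing safety data are not imputed.

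The date of the last dose varies. The schedule plans "Oral drug BID Days 1-14", but section 4.2.5 says that study drug "will be stopped at the time of hospital discharge if that occurs prior to day 15", and that drug stopped for an AE is not restarted. For discharged patients, section 8.1 plans calls around days 15 and 29 and an outpatient safety blood draw only afterwards ("day 30 - day 60 if possible, but up to day 100").

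**The concern.** A site that follows the last-dose rule would stop recording AEs before week 4 for anyone who leaves hospital or stops drug early. A crude 4-week proportion treats the unrecorded days as event-free. Discharge and toxicity stops both occur after randomization and may be affected by treatment, so the length of observation would depend on outcome. Sites that follow different statements would also collect different data. The transaminase and neutropenia endpoints, the secondary endpoint of grade III-V AEs or SAEs, and the interim rule of 3 or more excess events are exposed.

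**Working it through.** **Step 1: length of each window.** Let L be the day of the last dose. Under the last-dose rule, recording ends on day L + 14. The shortfall against 4 weeks is 28 − (L + 14) = 14 − L days.

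| Last dose (day) | Recording ends (day) | Days short of day 28 |
|---|---|---|
| 3 | 17 | 11 |
| 5 | 19 | 9 |
| 7 | 21 | 7 |
| 10 | 24 | 4 |
| 14 | 28 | 0 |

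Against day 29, each shortfall is one day longer. Only early stoppers lose observation time relative to 4 weeks. Under the other two statements there is no such shortfall, unless the patient withdraws.

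**Step 2: the plan's own stopping figures.** Section 15.1 gives the chance of 3 or more excess duvelisib events with 20 patients per arm. A normal approximation to the difference of two binomials reproduces its table:

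P = 1 − Φ{[3 − 20(pD − pP)] / √(20[pD(1 − pD) + pP(1 − pP)])}

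- Transaminases, 30% v 10%: the argument is (3 − 4)/√(20 × 0.30) = −0.408, so P = 65.85% (stated 65.8%).
- Transaminases, 10% v 10%: P = 5.69% (stated 5.7%).

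An exact binomial calculation gives 73% and 9.0% for these two cells. The approximation is kept below so that results compare with the plan's table.

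**Step 3: possible under-count.** The documents give no distribution of stopping or discharge times. Assume a constant hazard over 28 days. A true 4-week rate p is then seen in early stoppers as 1 − (1 − p)^((L + 14)/28). With L = 5 the exponent is 19/28:

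- p = 10%: 1 − 0.90^(19/28) = 6.9%. If half the arm stops then, the arm shows 0.5 × 10% + 0.5 × 6.9% = 8.4%.
- p = 24%: 1 − 0.76^(19/28) = 17.0%, and the arm shows 20.5%.

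For last doses on days 3 to 10 and 25% to 100% of the arm stopping early, a true 10% appears as 6.2% to 9.7%, and a true 24% as 15.3% to 23.2%.

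**Step 4: effect on the stopping rule.** Take true transaminase rates of 30% v 10%, with half of each arm stopping on day 5. The observed rates become 25.7% and 8.4%. The stopping probability falls from 65.8% to about 57.9% (exact: 73% to 65.9%), assuming full 4-week follow-up at the interim. No imbalance between arms is needed for this loss.

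**Step 5: bias between arms.** If early stopping is the same in both arms and true rates are equal, the expected difference is zero. With 60% v 40% stopping on day 5:

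- at a true 10% in both arms, 8.14% v 8.76%, a spurious 0.6 points;
- at a true 24% in both arms, 19.8% v 21.2%, a spurious 1.4 points.

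Swapping the split reverses the sign.

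**The case against.** The strongest reply is that nothing gives the last-dose rule precedence. Two other statements run longer, and section 15.2 keeps consenting patients in the study for safety and efficacy collection, with outpatient or telehealth follow-up to day 29. This stands: the firm finding is a contradiction, and truncation follows only if the shortest rule is applied. It does not dispose of the point. The shortest rule is the one that directs form entry. Later text in section 16.2 on SAEs arising after the reporting period also presupposes a bounded window. The rule that ends at withdrawal can itself end at an outcome, because section 12 lists the start of mechanical ventilation as an example of early withdrawal.

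Second, death and ventilation are followed to day 29 as the primary endpoint, and deaths are collected whether or not they are related to an AE. This stands, and it takes that safety endpoint largely out of the concern.

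Third, a reader might infer that safety rates are biased in duvelisib's favour. The documents do not support that. An event that itself stops the drug is already counted. Shorter stays on duvelisib would shorten its window, but section 5.6 allows drug to be discontinued at ventilation, and if duvelisib works that would shorten the placebo window.

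Fourth, the size depends on when events begin. If every onset fell in the first 14 days, the last-dose rule would miss none. This also stands.

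Finally, telephone questions cannot detect raised transaminases or neutropenia. For these the gap may start at discharge, so changing the AE window alone would not close it.

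**Conclusion.** The point holds as an internal contradiction with a conditional consequence. Sections 16.1 and 16.2 give three ends to AE recording. If the last-dose rule is applied, patients who stop before day 14 are observed for less than the 4 weeks analysed in section 15.1: 9 days less for a last dose on day 5. Laboratory and other AE/SAE incidence can then be under-counted, and the excess-event rule loses some ability to stop the trial. The percentages in the working illustrate this under an assumed constant hazard and assumed stopping patterns; they are not estimates for this trial. A difference between arms is a risk because observation time depends on post-randomization outcomes, but neither its size nor its sign can be derived from the documents. This should be corrected, but it is not a fatal flaw.

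**What to change.** - Set one AE and SAE recording window, from first dose to day 29, for every treated patient regardless of when study drug stops. Make section 16.1 and both statements in section 16.2 agree with it.
- Collect symptomatic AEs and SAEs from discharged patients at the day-15 and day-29 calls already planned in section 8.1.
- For transaminases and neutropenia, reconcile three passages: the schedule in section 1.2 (blood counts and chemistry abstracted as available in hospital), section 5.6 (panels on days 8, 15 and 29) and section 8.1 (outpatient draw after day 29). State that events after discharge are ascertained only where blood results exist, and report by arm how many patients have laboratory data through week 4.

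The cost is protocol wording, a few extra questions on existing calls and slightly more AE data entry.

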- Due to the wide array of symptoms experienced by patients hospitalized with COVID-19, it is not feasible or informative to record and assess all possible symptoms and lab test results for AE/SAE grading in this study. Hence AE/SAE grading and reporting will be limited to lab tests that might reflect effects of study drug exposure including bilirubin, ALT, ALK PHOS, AST, leukopenia, lymphopenia, anemia, and thrombocytopenia. Symptomatic AE/SAE grading and reporting will focus on the following: diarrhea, bradycardia, symptoms requiring ICU admission and mechanical ventilation, symptoms requiring repeat hospitalization, or death. Non-clinically relevant AEs (Grade 1) will not be included on AE logs or AE reporting documents.

Classification of an Adverse Event

Severity of Event

For both AE's and SAE's the investigator must assess the severity of the event. The severity of the event will be graded based off the patient's symptoms using the Common Terminology Criteria for Adverse Events (CTCAE Version 5.0):

https://ctep.cancer.gov/protocoldevelopment/electronic_applications/docs/CTCAE_v5_Quick_Reference_5x7.pdf.

The terms "severe" and "serious" are not synonymous. Severity refers to the intensity of an AE (as in mild, moderate, or severe pain); the event itself may be of relatively minor medical significance (such as severe headache). "Serious" is a regulatory definition and is based on patient or event outcome or action criteria usually associated with events that pose a threat to a patient's life or vital functions. Seriousness (not severity) serves as the guide for defining regulatory reporting obligations

Relationship to Study Intervention

All adverse events (AEs) must have their relationship to study intervention assessed by the clinician who examines and evaluates the participant based on temporal relationship and his/her clinical judgment. The degree of certainty about causality will be graded using the categories below. In a clinical trial, the study product must always be suspect.

Expectedness

Principal Investigator will be responsible for determining whether an adverse event (AE) is expected or unexpected.

An **expected** adverse event is those that have previously identified resulting from administration of the study drug. These include, but not limited to, AE's that are listed in the AE list, stated on the informed consent document or listed on the investigator's brochure.

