7. Outcome (not recovered/not resolved, recovered/resolved, recovering/resolving, recovered/resolved with sequelae, fatal, unknown)

Protocol Title: Duvelisib Ameliorates Manifestations of Pneumonia in Established Novel Coronavirus Infection (DAMPEN-CI)

If the event worsens the event should be reported a second time in the CRF noting the start date when the event worsens in toxicity. For grade 3 and 4 adverse events only, if improvement to a lower grade is determined a new entry for this event should be reported in the CRF noting the start date when the event improved from having been Grade 3 or Grade 4. For phase I studies any AE that constitutes a DLT should be reported like a grade 3 and 4 adverse event. All adverse events should be treated appropriately. If a concomitant medication or non-drug therapy is given, this action should be recorded on the Adverse Event CRF.

Once an adverse event is detected, it should be followed until its resolution or until it is judged to be permanent, and assessment should be made at each visit (or more frequently, if necessary) of any changes in severity, the suspected relationship to the study treatment, the interventions required to treat it, and the outcome. Laboratory abnormalities that constitute an Adverse event in their own right (are considered clinically significant, induce clinical signs or symptoms, require concomitant therapy or require changes in study treatment), should be recorded on the Adverse Events CRF.

Laboratory abnormalities, that do not meet the definition of an adverse event, should not be reported as adverse events.

A Grade 3 or 4 event (severe) as per CTCAE does not automatically indicate a SAE unless it meets the definition of serious as defined below and/or as per investigator's discretion. A dose-hold or medication for the lab abnormality may be required by the protocol in which case the lab abnormality would still, by definition, be an adverse event and must be reported as such. Any serious adverse event, or follow up to a serious adverse event, including death due to any cause whether or not related to the study drug, must be **submitted on an SAE form** and assessed by PI in order to determine reporting criteria to regulatory authorities, IRB, DSMC, FDA.

All serious adverse events collected during this time frame will also be reported to Verastem.

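### Asymptomatic, untreated Grade 3/4 liver-enzyme or neutrophil values can drop out of the adverse-event counts that the IDMC reviews monthly and that form the Grade III-V endpoint

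*Combined protocol and SAP*

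**What the plan says.** Three parts of section 16.2 govern when a laboratory value becomes an adverse event.

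- **Definition of Adverse Events.** The principal investigator reviews each abnormality: "If the abnormality is deemed to be clinically significant, then the adverse event will be reported".
- **Documenting Adverse Events.** This part is wider. Abnormalities count if they "are considered clinically significant, induce clinical signs or symptoms, require concomitant therapy or require changes in study treatment". If the protocol requires a dose-hold or medication, a further clause applies: "in which case the lab abnormality would still, by definition, be an adverse event and must be reported as such". For everything else, "Laboratory abnormalities, that do not meet the definition of an adverse event, should not be reported as adverse events".
- **Study-Specific AE/SAE Reporting.** Here "AE/SAE grading and reporting will be limited to lab tests that might reflect effects of study drug exposure". The list names ALT, AST, bilirubin, alkaline phosphatase, leukopenia, lymphopenia, anemia and thrombocytopenia. Neutropenia is not named. Only Grade 1 is described as not clinically relevant and kept off the logs.

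On the use of the counts, section 15.1 (Stopping Rule for Safety) has the IDMC review each month "the number of Grade 3 and/or Grade 4 adverse events in each arm, including neutropenia and elevated transaminases" and consider stopping or suspending accrual. The Grade III-V secondary endpoint (1.1 and section 2) is also worded as adverse events. The interim rule and the Analysis of Safety Data in 15.1 are stated as incidences of Grade 3 or higher transaminase elevation and of neutropenia, with no data source given.

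The raw values are collected separately. The Schedule of Assessments has "Clinical Labs: Record data in eCRF (REDCap) during hospitalization", covering CBC with differential and the metabolic panel, abstracted as available. Section 5.6 schedules laboratory tests at screening and on days 1, 8, 15 and 29.

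**The concern.** Raised transaminases and low neutrophil counts are often silent. A Grade 3 ALT in a patient with no attributable symptoms, no treatment for it and no change in study drug becomes an adverse event only if someone judges it clinically significant. The AE-based counts would then measure opinion as well as CTCAE grade, although grade is what the monthly review and the secondary endpoint name.

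Sites could also follow different parts of 16.2. One would log every Grade 2 or higher value of a listed test. Another would log only those judged significant. For neutropenia, a stopping endpoint, the study-specific list gives no explicit instruction.

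A filter applied by blinded staff would be expected to remove events from both arms. That leaves the ratio of rates roughly unchanged but shrinks the absolute excess, which is what an IDMC looking at small counts sees. A real hepatic or neutrophil signal would be harder to detect.

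**Working it through.** **1. Can a Grade 3/4 value be left out when the plan is followed as written?** Take an asymptomatic, untreated Grade 3 ALT and go through the triggers.

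- Signs or symptoms: none. Concomitant therapy: none.
- Change in study treatment, or a protocol-required hold: section 4.2.5 says drug can be stopped at Grade 3/4, and section 5.3 leaves modification or discontinuation to the investigator. The documents contain no mandatory hold for such a value, so the by-definition clause is not reached.
- Clinical significance: a judgement.

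Only the judgement remains. No statement in 15.1 or 16.2 makes every Grade 3/4 ALT, AST or neutrophil value count automatically.

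**2. Which counts are exposed?**

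| Count | Worded as | Exposed? |
|---|---|---|
| Monthly IDMC review (15.1) | Grade 3/4 adverse events | Yes, on the wording |
| Grade III-V secondary endpoint (1.1, 2) | Adverse events or SAEs | Yes, on the wording |
| Interim 3-excess rule (15.1) | Incidence, no source named | Only if fed from AE forms |
| Final safety comparison (15.1) | Incidence, no source named | Only if fed from AE forms |

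**3. Reproducing the plan's table.** Inputs from 15.1: n = 20 per arm, a trigger of 3 or more excess events, and placebo rates of 10% (transaminases) and 24% (neutropenia). With duvelisib rate pD and placebo rate pP, the normal approximation without continuity correction is

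P = 1 − Φ( [3 − 20(pD − pP)] / √(20[pD(1 − pD) + pP(1 − pP)]) ).

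For 10% against 30%: (3 − 4)/√(20 × (0.21 + 0.09)) = −1/√6 = −0.408, so P = 65.8%, as tabulated. All 21 cells of the table reproduce within 0.1 point. The exact probability, summing the two binomials over all pairs with an excess of at least 3, is higher: 73.0% for this cell, and up to about 8 points above the table elsewhere. Both versions are shown below.

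**4. Illustration if the interim rule were fed from AE forms.** Multiply both true rates by a capture share s, equal in the two arms. The documents give no value for s; 100%, 75% and 50% are assumptions. For 10% against 30% at s = 0.75, the rates become 7.5% and 22.5%, and the approximation gives (3 − 3)/… = 0, so P = 50.0%.

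| True rates, placebo vs duvelisib | Method | s = 100% | 75% | 50% |
|---|---|---|---|---|
| Transaminases 10% vs 30% | exact | 73.0% | 58.6% | 38.3% |
| | plan's approximation | 65.8% | 50.0% | 29.6% |
| Transaminases 10% vs 10% (false trigger) | exact | 9.0% | 6.3% | 3.4% |
| | plan's approximation | 5.7% | 3.6% | 1.5% |
| Neutropenia 24% vs 50% | exact | 82.1% | 69.6% | 51.5% |
| | plan's approximation | 77.3% | 62.8% | 43.4% |
| Neutropenia 24% vs 24% (false trigger) | exact | 17.6% | 15.0% | 10.8% |
| | plan's approximation | 13.3% | 10.8% | 7.2% |

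The same thinning applied to the final Fisher test (40 per arm, 10% vs 30%, two-sided 5% assumed because 15.1 sets no level for this test) gives power of 53%, 37% and 18%.

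**The case against.** The strongest reply is that the study-specific part of 16.2 should prevail over generic text. The sentence on not reporting abnormalities sits among wording that also refers to phase I studies and dose-limiting toxicities, whereas the study-specific part names ALT and AST and treats only Grade 1 as not clinically relevant. On that reading a Grade 3 ALT is logged. This is a fair reading, but 16.2 does not say which part prevails, and it does not help neutropenia, which the list omits. Leukopenia is listed and the list may not be exhaustive, so that omission is a gap and not an exclusion.

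Three stronger readings are tempting, and the documents do not support them.

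- **That a laboratory value is an adverse event only if the investigator calls it clinically significant.** There are three other triggers, plus the by-definition clause. The gap is confined to values that meet none of these.
- **That the interim stopping rule and final safety comparison are undercounted.** Both are stated as incidences, and the laboratory values are in REDCap independently of AE status. Undercounting there is possible, not established.
- **That values put down to COVID-19 may be omitted.** Section 16.1 records adverse events regardless of relationship and also reviews Grade 3 to 5 events judged unrelated. Attribution is not a ground for omission; only the significance judgement is.

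It is also fair to say that the monthly review is discretionary with no numeric trigger, that nobody knows how many Grade 3/4 values would be judged not significant, and that filtering lowers false triggers as well as true ones.

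**Conclusion.** The concern holds in a limited form. As written, 16.2 allows a silent, untreated Grade 3/4 ALT, AST or neutrophil value to be absent from the monthly IDMC counts and the Grade III-V endpoint, and its own parts disagree on whether that should happen. This rests on the wording alone.

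The effect on the interim rule and final analysis is conditional on AE forms being their source. If they are, the exact chance of triggering at transaminases 10% vs 30% falls by about 14 points at 75% capture (73.0 − 58.6 = 14.4) and about 35 points at 50% (73.0 − 38.3 = 34.7), with a smaller drop in false triggers. Those sizes depend wholly on the assumed capture share and on its being equal in both arms. They do not quantify the monthly review, which has no numeric rule.

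The remedy uses data the trial already collects, so the change is worth making even though the size of the loss is unknown.

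**What to change.** - **Section 15.1.** State that the transaminase and neutropenia counts for the monthly IDMC tables, the interim rule and the final safety analysis are derived by program, per patient, from all CTCAE v5.0 Grade 3 or higher ALT, AST and ANC values in REDCap, whatever their adverse-event designation. The same sentence should attach the grade explicitly to neutropenia, which the present wording leaves unclear.
- **Section 16.2.** Add neutropenia/ANC to the study-specific laboratory list. Reconcile the three parts so that a Grade 3 or higher value of a listed test is recorded as an adverse event regardless of the significance judgement, which also settles the Grade III-V endpoint. The judgement can stay for lower grades.

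The cost is a sentence in 15.1, a short edit to 16.2 and a small derivation program. There are two downsides: some disease-related elevations will be counted in both arms, and values abstracted as available leave gaps, though these do not depend on a significance judgement. No treatment rule changes.
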